10.8 Adverse Events and Serious Adverse Events

The investigator is responsible for the detection and documentation of events meeting the criteria and definition of an AE or serious adverse event (SAE) as provided in this protocol.

10.8.1 Definition of an Adverse Event (AE)

An AE is any untoward medical occurrence in a clinical investigation subject administered a pharmaceutical product and which does not necessarily have to have a causal relationship with this treatment.

An AE can therefore be any unfavorable and unintended sign (including clinically significant abnormal laboratory finding), symptom, disease, or exacerbation of a pre-existing condition temporally associated with the use of study drug, whether or not related to the study drug.

Disease progression should not be recorded as an AE/SAE. New or increasing symptoms related to disease progression should be reported as an AE or AEs. When possible, the primary diagnosis of the event meeting SAE criteria should be recorded as the AE/SAE term. (For instance, if a subject is hospitalized for shortness of breath and it is confirmed that this is a symptom of a malignant pleural effusion, then malignant pleural effusion should be reported as the event term, rather than disease progression).

10.8.2 Observation and Recording of AEs

AEs that occur on the parent study and are ongoing at the time of entry into the rollover study will be recorded as medical history. Any such AE that worsens on the rollover study should be recorded as a new AE at the worsened severity.

Study personnel will assess AEs at every visit. The date of onset and resolution (if applicable) of the AE will be documented in the source documents and on the appropriate eCRF page. The Investigator will monitor all AEs to the final study visit or to a satisfactory resolution if the AE is ongoing.

All AEs will be recorded from the time of signed informed consent until the End-of-study visit (28 days \pm 7 days after the last dose of study drug[s]) and are to be recorded on the appropriate AE pages in the eCRF and in source documents. AEs for the End-of-study visit may be collected by a telephone contact if the subject is not able to attend an on-site End-of-study visit. Where possible, a diagnosis rather than a list of symptoms should be recorded. If a diagnosis has not been made, then each symptom should be listed individually.

All study drug related AEs/SAEs (see [Section 10.8.4](#) for definition) will be followed to resolution (the subject's health has returned to his/her baseline status or all variables have returned to normal), or until new therapy initiated. Where appropriate, medical tests and examinations will be performed to document resolution of the event(s).

SAEs will be reported as outlined in [Section 10.9](#) and recorded in the AE eCRF.

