| Neuropathy | Grade 2 | 
 Withhold study drug(s) until resolution to Grade 0-1; if symptoms persist 2¹ 6 weeks, discuss subject continuation with the Medical Monitor. When symptoms resolve to Grade 0-1, resume vopratelimab. If symptoms do not recur after 1 cycle of vopratelimab, resume ipilimumab/nivolumab therapy.^b Permanently discontinue study drug(s) for related reactions lasting 6 weeks or longer or if the subject is unable to reduce the corticosteroid dose to less than 7.5 mg prednisone or equivalent per day. | 
(peripheral neuropathy) Initial observation OR initiate prednisone 0.5-1 mg/kg (if progressing from mild). Neurontin, pregabalin, or duloxetine for pain
 
(Autonomic neuropathy) Initial observation OR initiate prednisone 0.5-1 mg/kg (if progressing from mild). Neurologic consultation
 |
| | Grade 3 or 4 | 
 Permanently discontinue study drug(s). | 
(Peripheral neuropathy) Neurologic consultation Initiate IV methylprednisolone 2-4 mg/kg Monitor pulmonary function, concurrent autonomic dysfunction, neuropathic pain, constipation/ileus. Offer frequent neurochecks
 
(Autonomic neuropathy) Initiate methylprednisolone 1g IV daily for 3 days followed by oral corticosteroid taper Neurologic consultation
 |
| Encephalitis | New-onset moderate or severe neurologic signs or symptoms | 
 Permanently discontinue study drug(s). | 
If etiologies other than immune-mediated adverse events are ruled out, permanently discontinue study drug(s) and administer 1-2 mg/kg/day prednisone equivalents^a Administer concurrent IV acyclovir until PCR results obtained and negative
 |
| | Immune-mediated encephalitis | 
 Permanently discontinue study drug(s). | 
1-2 mg/kg/day prednisone equivalents^a If limited or no improvement, may offer rituximab or plasmapheresis
 |

| Adverse Event | Toxicity Grade | Dose Modification | Recommended Management ^a |
|-----------------|---------------------------|---|---|

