9 OVERALL STUDY ASSESSMENTS

Duration of participation on this study will be dependent on the amount of time a subject derives clinical benefit. An End-of-study visit will be performed 28 days (\pm 7 days) after the last dose of study treatment.

9.1 Rollover Entry/Cycle 1 Day 1

Enrollment into the rollover study should occur upon exit from the parent study to avoid any interruptions in study treatment administration.

All assessments should be performed prior to vopratelimab dosing, unless otherwise noted.

- Signing of informed consent form.
- Review eligibility criteria to determine whether a subject may enter the rollover study.
- Physical examination.
- Vital signs pre-and post-infusion.
- Weight.
- Serum or urine pregnancy test for women of childbearing potential. The pregnancy test will not be required for women who are surgically sterile or who are greater than 1 year post-menopausal.
- Laboratory assessments including hematology and chemistry; additional laboratory measurements may be performed in accordance with institutional guidelines.
- Pharmacodynamic biomarkers; Collection of samples may be discontinued at any time per the Sponsor's discretion.
- Record ongoing concomitant medications and AEs.
- Study treatment (vopratelimab \pm partner drug) administration on the same dose and schedule as a subject was receiving at the time of discontinuation from the parent study. Study drug administration between the parent and rollover study should be maintained per the dose and schedule on the parent study. Any changes to the dose and schedule of vopratelimab must be in accordance with a dose and schedule previously shown to be safe and well tolerated and must be discussed with the medical monitor. Any changes to the dose and schedule of nivolumab or ipilimumab must be discussed with the medical monitor.

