## 3. STUDY ENDPOINTS

### 3.1 PRIMARY ENDPOINT

- Incidence and severity of treatment-emergent adverse events (TEAEs), serious TEAEs, and discontinuation due to adverse events (AEs) evaluated using National Cancer Institute (NCI) Common Technology Criteria for Adverse Events (CTCAE) version 5.0 and death

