### 6.6.1 ADVERSE EVENTS

### 6.6.1.1 ADVERSE EVENT DEFINITIONS

Adverse events will be coded into standardized terminology according to the Medical Dictionary for Regulatory Activities (MedDRA) dictionary v23.0 or higher. Severity of AE will be graded according to National Cancer Institute Common Terminology Criteria for Adverse Events Version 5.0 (NCI CTCAE, v5.0).

- Treatment-Emergent Adverse Events (TEAEs) are designated as events that occur after the start of study drug(s), and were not observed prior to start of treatment; Or if the event was observed prior to the start of study drug but worsened after the start of study drug in the rollover study.
- Treatment Related TEAEs will include those TEAEs which are considered related to study drugs as designated by the investigator and/or Sponsor.
- Serious adverse events (SAEs) will include all events classified as serious on the eCRF. The electronic database used to enter data at the site will be deemed as the source of record for adverse event information. The safety and pharmacovigilance database will be reconciled against the EDC.
- Immune-related adverse events (irAEs) are unique side effects typically seen after dosing with checkpoint inhibitors and are derived based on eCRF irAE flag. Some of the most common irAEs include: pneumonitis, colitis, hepatitis, endocrinopathy , adrenal insufficiency, hypothyroidism and hyperthyroidism, , nephritis, dermatitis, and neuropathy Summary of Adverse Events

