### 6.6.1.2 SUMMARY OF ADVERSE EVENTS

Adverse events (AEs) will be listed. Listings will be created by categories for AEs as outlined below:

- All adverse events (AEs) with flags for treatment emergent adverse events (TEAEs) and flags of relatedness to study drug(s)
- SAEs with flags for treatment emergent adverse events (TEAEs) and flags of relatedness to study drug(s)
- Immune related adverse events (irAEs)
- Infusion related reactions (IRRs)
- TEAEs leading to death
- TEAEs leading to study drug interruption, reduction, hold or permanent study drug discontinuation

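### A toxicity carried over from the parent study that leads to a hold or stop at unchanged grade has no rollover AE record, so AE-based and disposition counts of discontinuation can disagree

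*Protocol*

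**What the plan says.** - **Recording rule.** Protocol 10.8.2: "AEs that occur on the parent study and are ongoing at the time of entry into the rollover study will be recorded as medical history". The one stated exception follows: "Any such AE that worsens on the rollover study should be recorded as a new AE at the worsened severity". There is no exception for an unchanged event that leads to action on study drug.
- **TEAE definition.** SAP 6.6.1.1 covers events that begin after the start of study drug and "were not observed prior to start of treatment", plus earlier events that worsened in the rollover.
- **Outputs.** The action-taken listing in SAP 6.6.1.2 is limited to "TEAEs leading to study drug interruption, reduction, hold or permanent study drug discontinuation". The overview table counts the same categories.
- **Primary endpoint.** SAP 3.1 words the component more broadly: "discontinuation due to adverse events (AEs) evaluated using National Cancer Institute (NCI" CTCAE version 5.0. It says AEs, not TEAEs.
- **Other routes.** Protocol 8 puts the primary reason for withdrawal on a separate eCRF form. Protocol 11.1 derives the discontinuation reason for the investigational drug. SAP 6.4.1 summarises reasons for stopping treatment with no TEAE condition, and SAP 6.4.3 lists dose modifications with their reason.

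**The concern.** The sole primary objective is the long-term safety of continued treatment. Persisting toxicity that eventually makes a subject or investigator stop is central to that question. The recording rule and the TEAE restriction together count new onsets and grade increases, but not an old event that becomes treatment-limiting because it lasts.

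At stake is whether the AE data can show these discontinuations with their grade, relationship and immune-related status. If they cannot, a reader of the AE overview sees fewer AE-linked discontinuations than occurred. A reader who compares it with the disposition table may find a different number and no AE record to explain it.

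**Working it through.** The documents give no sample size, event rate or count, so there is no plan figure to reproduce. The check follows one event through the plan: a parent-study AE, ongoing at entry, never worse in grade, that leads to a hold or discontinuation in the rollover.

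**Step 1. Where the event appears**

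| Output | Does the event appear? |
|---|---|
| Listing of all AEs (SAP 6.6.1.2) | No. Protocol 10.8.2 creates no rollover AE record. |
| Action-taken listing (SAP 6.6.1.2) | No. There is no AE record, and the listing is limited to TEAEs. |
| irAE listing (SAP 6.6.1.1 and 6.6.1.2) | No. It is derived from an eCRF flag, and none is described for medical history. |
| AE overview table (SAP 6.6.1.2) | No. It uses the same categories. |
| Medical history listing (SAP 6.4.5) | The event yes; no action taken or relationship is described. |
| Disposition summary (SAP 6.4.1) | The reason yes; no grade, relationship or irAE status is described. |
| Dosing listing (SAP 6.4.3) | The reason for modification yes; no link to a graded event is described. |

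**Step 2. Does the reading of the TEAE definition matter?** The first limb does not say whether treatment starts in the parent study or the rollover, and SAP 6.1.1 sets baseline at the parent baseline. On the rollover reading the event is not a TEAE. On the parent reading it might be one, but it still sits in medical history and not on the AE pages. The gap exists either way.

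**Step 3. Can the case arise?** Yes.
- Protocol 5.1 bars only ongoing toxicity that would preclude dosing.
- Protocol 6.1.2.2 lets subjects keep their parent-study medications.
- Several endocrine rows of Table 1 tie the hold to stabilisation on hormone replacement and not to a fall in grade, so controlled toxicity can be present at entry.
- Protocol 8.1 accepts withdrawal for an AE because of its nature or need for treatment, with no grade change required.

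**Step 4. Do the other routes deliver the endpoint?** Only in part. SAP 3.1 wants the component assessed by CTCAE, and a disposition reason is described without a grade. Protocol 11.1 refers to the investigational drug, which Protocol 6.1 defines as vopratelimab, so a stop of the partner drug alone is not clearly covered there. Neither document says whether the endpoint is counted from the disposition data or from the TEAE listing.

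**Step 5. Size.** With N treated subjects, one missed discontinuation changes the AE-based proportion by 1/N. For assumed N: 1/5 = 20 percentage points, 1/10 = 10, 1/20 = 5.

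**The case against.** Several stronger readings are tempting, and the documents do not support them.

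- **That such events vanish from the primary endpoint.** The endpoint says AEs without a TEAE limit, and the reason for stopping survives in Protocol 8, Protocol 11.1 and SAP 6.4.1. What is lost is the AE-based display and the link to a graded, attributed event.
- **That deaths are missed.** A fatal AE is Grade 5 in Protocol Table 2, so it has worsened, becomes a new AE and meets the second TEAE limb. Protocol 10.8.5 also requires the event that caused death to be recorded, and SAP 6.4.1 summarises cause of death.
- **That Table 1's duration rules prove the case.** The Grade 2 neuropathy row includes "Permanently discontinue study drug(s) for related reactions lasting 6 weeks or longer or if the subject is unable to reduce the corticosteroid dose". But that row withholds drug until Grade 0-1, and Protocol 5.1 and 5.2 require current dosing at entry. Such a subject would normally enter at Grade 0-1, and a later Grade 2 would be a worsening. The rule on prolonged prednisone use is narrowed by the steroid restrictions in Protocol 6.1.1 and 6.1.2.1 and by footnote b of Table 1. It is not closed, because Protocol 6.1.2.2 permits oral steroids; those sections need reconciling in their own right.
- **That Protocol 9.1 contradicts 10.8.2.** The entry-visit instruction, "Record ongoing concomitant medications and AEs", does not name a form, so the two can be read together.
- **That the duration and outcome of chronic AEs are cut off at the study boundary.** Protocol 10.8.2 asks for related AEs to be followed to resolution, and no follow-up is described for a medical-history entry. But the parent protocol and database, which may hold that follow-up, are not available here.

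It is also fair to say that filing existing events as history avoids counting one event in two studies, and that this is a descriptive, listing-based rollover with no hypothesis test. Both points argue for a small change. Neither supplies the missing AE record or names the source of the endpoint.

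**Conclusion.** The point holds in a limited form and is worth correcting. Followed exactly, the plan under-counts AE-linked holds and discontinuations whenever the cause is a carried-over event at unchanged grade, and it leaves the AE-based and disposition counts free to disagree. The endpoint component is worded for AEs, while its only AE-based display is restricted to TEAEs.

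The frequency cannot be estimated from the documents. The entry rules and the Table 1 withholding rules make it low, mainly discretionary stops for stable low-grade or controlled toxicity. Each missed discontinuation costs 1/N in the AE-based proportion. This is not evidence that the primary endpoint as a whole is unusable, since the discontinuation itself is still captured.

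The conclusion assumes that sites apply 10.8.2 as written and that the eCRF has no unstated link from medical history to action taken.

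**What to change.** **Protocol 10.8.2.** Keep the medical-history rule and add one exception. Any AE ongoing at entry that leads to interruption, hold, reduction or discontinuation of any study drug in the rollover is entered on the AE eCRF whether or not its grade changes. Record the parent-study onset date, grade, relationship, irAE flag and an ongoing-at-entry mark. The event is not a TEAE unless it worsens.

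**SAP 6.6.1.2.** Base the action-taken listing and the matching overview row on all AEs, with TEAE as a flag. Show carried-over events as a separate row. State that this output is the source for the discontinuation component in SAP 3.1, and that it is reconciled with the disposition reasons.

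**Cost.** One eCRF flag and a few sentences in each document. The reported number of AE discontinuations may be slightly higher. No treatment rule changes, the TEAE definition stays as it is, and there is no need to move every ongoing parent-study AE onto the rollover AE pages.

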10.8.3 Grading and Severity

Grade refers to the severity of the AE/SAE. Severity will be assessed in this study using the National Cancer Institute (NCI) Common Terminology Criteria for Adverse Events (CTCAE), version 5.0 (see [Appendix 3](#)).

In the event that an AE is not covered by the CTCAE, the assessment of severity will be determined by using the CTCAE general guideline:

Table 2: Grading for Events Not Covered By the CTCAE

| | |
|---------|--|
| Grade 1 | Mild; asymptomatic or mild symptoms; clinical or diagnostic observations only; intervention not indicated. |
| Grade 2 | Moderate; minimal, local or noninvasive intervention indicated; limiting age-appropriate instrumental ADL*. |
| Grade 3 | Severe or medically significant but not immediately life-threatening; hospitalization or prolongation of hospitalization indicated; disabling; limiting self-care ADL**. |
| Grade 4 | Life-threatening consequences; urgent intervention indicated. |
| Grade 5 | Death related to AE |

Activities of Daily Living (ADL)

*Instrumental ADL refer to preparing meals, shopping for groceries or clothes, using the telephone, managing money, etc.

**Self-care ADL refer to bathing, dressing and undressing, feeding self, using the toilet, taking medications, and not bedridden.

The Investigator will evaluate all AEs as to their severity.

- An AE that is assessed as severe should not be confused with an SAE. Severity is a category used for rating the intensity of an event; both AEs and SAEs can be assessed as severe. An event is described as 'serious' when it meets one of the pre-defined outcomes as described in [Section 10.9](#).

Worsening of a pre-treatment event, after initiation of study drug(s) must be recorded as a new AE.

10.8.4 Relationship Categorization

An Investigator qualified in medicine must make the determination of relationship to study drug for each AE/SAE. The Investigator should decide whether, in his or her medical judgment there is a reasonable possibility that the event may have been caused by the study drug. If no valid reason exists for suggesting a relationship, the AE/SAE should be classified as “definitely not”. If there is a valid reason, even if undetermined or untested, for suspecting a possible cause-and-effect relationship between the study drug and the occurrence of the AE/SAE, the AE/SAE should be considered “possibly related”. [Table 3](#) should be used for guidance in the determination of relationship:

Table 3: Guidance in Determining the Relationship of an Adverse Event

| Relationship | Definition |
|---------------------|--|
| Unrelated | There is no association between study drug and the reported event. |
| Related | 
The event follows a reasonable temporal sequence from the time of study drug administration and/or follows a known response pattern to the study drug, but could also have been produced by other factors.
 
A causal relationship also exists between study drug administration and the AE if other conditions (e.g., concurrent illness, progression/expression of disease state, or concurrent medication reaction) do not appear to explain the event.
 |

If the causal relationship between an AE/SAE and study drug(s) is determined to be possibly or probably related, the event will be considered to be related to vopratelimab per investigator assessment for the purposes of expedited regulatory reporting. Note: “Cannot be ruled out” is not a basis for the assessment of possibly or probably related.

10.8.5 Outcome Categorization

Outcome of an AE/SAE may be classified as resolved, resolved with sequelae, unresolved, or fatal. Death is an outcome of an event. The event that resulted in death must be recorded on the appropriate eCRF.

10.8.6 Clinical Laboratory Evaluations

A clinical laboratory AE is any laboratory value that is considered clinically significant by the Investigator and has caused a medical intervention or accompanied by clinical symptoms. Laboratory abnormalities that have not required medical intervention should not be recorded as AEs and will be captured and reported in the laboratory section of the clinical study report. If a

medical intervention occurs, it should be recorded as a treatment with the abnormal laboratory finding as the AE.

The Investigator should decide, based upon the AE criteria and the clinical condition of the subject, whether a change in a laboratory parameter is clinically significant and therefore represents an AE.

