10.1 Physical Examination

At all visits, a targeted physical examination will be performed per institutional guidelines. Clinically significant physical examination data will be recorded on the eCRF as AEs, as appropriate.

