10.2 Vital Signs

Measurements of vital signs include blood pressure, temperature, heart rate, respiratory rate, and oxygen saturation. Vital signs should be taken prior to and at the end of each vopratelimab infusion. Clinically significant vital sign data will be recorded on the eCRF as AEs, as appropriate.

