10.5 Clinical Laboratory Evaluations

Clinical laboratory assays will include chemistry and hematology, as well as any other measurements according to institutional standard of care guidelines, performed at local laboratories according to the laboratory's normal procedures. Abnormal laboratory values that are unexpected and not explained by the subject's clinical condition should be repeated until confirmed, explained, or resolved. In the judgment of the Investigator, any clinically significant changes will be recorded on the eCRF as an AE.

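### Protocol 10.8.6 bars untreated laboratory abnormalities from the AE record, against 10.5, 10.8.1 and its own wording, so TEAE counts can miss clinically significant findings

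*Protocol*

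**What the plan says.** Three protocol sections decide when a laboratory abnormality becomes an AE.

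- **10.5** leaves it to the investigator's judgement and then is unconditional: "any clinically significant changes will be recorded on the eCRF as an AE".
- **10.8.1** defines an AE as covering any unfavourable sign, "including clinically significant abnormal laboratory finding".
- **10.8.6** contains three statements. Its first sentence describes a laboratory AE as a value "considered clinically significant by the Investigator and has caused a medical intervention or accompanied by clinical symptoms". Its second sentence says: "Laboratory abnormalities that have not required medical intervention should not be recorded as AEs", and sends those abnormalities to the laboratory part of the study report. Its closing sentence has the investigator decide, "based upon the AE criteria and the clinical condition of the subject", whether a change is clinically significant and for that reason an AE.

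The other routine examinations carry no intervention test. For physical examination (10.1): "Clinically significant physical examination data will be recorded on the eCRF as AEs, as appropriate". For vital signs (10.2): "Clinically significant vital sign data will be recorded on the eCRF as AEs, as appropriate".

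The primary endpoint in SAP 3.1 is built from recorded AEs: TEAEs, serious TEAEs, discontinuations due to AEs, and death. SAP 6.6.1.2 plans AE listings and one overview table. SAP 6.6.2 plans laboratory listings showing results, normal ranges and CTCAE grade.

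**The concern.** A site cannot follow 10.5 and the second sentence of 10.8.6 at once. Given the same clinically significant, untreated value, one site would open an AE record and another would not. Every disagreement runs the same way: the restrictive sentence removes an AE and never adds one.

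The consequence reaches the primary endpoint because TEAE counts come from AE pages. Programming cannot restore an AE that was never entered. The laboratory listing keeps the value and its grade, but SAP 6.6.2 names no field for clinical significance, relationship to study drug or action taken.

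**Working it through.** The plan states no figure to reproduce and gives no event rates, so the check sets the rules side by side. Take a laboratory value that the investigator has judged clinically significant, and apply each rule to the four combinations of medical intervention (yes/no) and symptoms (yes/no).

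| Case | 10.5 and 10.8.1 | 10.8.6, first sentence | 10.8.6, second sentence | 10.8.6, closing sentence (plain reading) |
|---|---|---|---|---|
| Intervention and symptoms | AE | AE | not barred | AE |
| Intervention only | AE | AE | not barred | AE |
| Symptoms only | AE | AE | barred | AE |
| Neither | AE | not AE | barred | AE |

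1. **Conflict with 10.5 and 10.8.1.** The second sentence disagrees in the last two rows: 2 of 4, exactly the cases without intervention.
2. **Conflict inside 10.8.6.** In the symptoms-only row the first sentence says AE and the second bars it. That contradiction is certain (1 of 4). On the plain reading of the closing sentence, the last row is contradictory as well (2 of 4). If "based upon the AE criteria and the clinical condition of the subject" is taken to import the first sentence's test, the last row is consistent within 10.8.6 but still conflicts with 10.5 and 10.8.1.
3. **What is lost in practice.** In the symptoms-only row, the symptom is an AE in its own right under 10.8.1, and 10.8.2 has symptoms listed individually where there is no diagnosis. The subject stays in the AE data, though the laboratory term may not. The clear loss is the last row.
4. **Undefined term.** The protocol does not define medical intervention. Section 10.8.6 says an intervention is to be entered as a treatment, so a study-drug hold alone is not clearly one. Table 1 nevertheless ties holding or stopping study drug to laboratory thresholds (AST/ALT, bilirubin, creatinine), and its hepatitis rows allow investigator discretion as an alternative to corticosteroids. An abnormality whose only consequence was a hold or a stop could therefore fall on either side of the bar.
5. **Effect of a partial repair.** Deleting only the second sentence leaves the first sentence in conflict with 10.5 and 10.8.1 in the last row (1 of 4). Aligning the first sentence as well brings the conflicts to 0 of 4.

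**The case against.** The strongest defence is that 10.8.6 is the specific section and narrows the general wording of 10.5 and 10.8.1, deliberately keeping minor laboratory noise off the AE pages. That would work if 10.8.6 stated one rule. It does not: its second sentence cancels the symptom route that its first sentence opens.

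Other points on that side stand, at least in part:

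- The four cases are logical combinations, not events. Two of four says nothing about how many AEs would be missed.
- Sections 10.1 and 10.2 leave room for discretion, so they support the broad rule only weakly. The same holds for the Grade 1 wording in Table 2 of 10.8.3 ("clinical or diagnostic observations only; intervention not indicated"). That table grades events already accepted as AEs. It shows only that the protocol does not regard an untreated AE as a contradiction in terms.
- A narrower rule, clinical significance plus intervention or symptoms, would also end the contradiction if written into all three sections. The reason to prefer clinical significance alone is that 10.5, 10.8.1 and the closing sentence of 10.8.6 already state it.
- The study is descriptive, with no hypothesis test, so no error rate or power is affected.

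**Conclusion.** The recording rule is contradictory as written and should be corrected. For clinically significant laboratory values the rules conflict whenever there was no medical intervention. The direction is under-recording. The likely loss is mainly untreated, asymptomatic, non-serious abnormalities, possibly with some that led only to a study-drug hold. No size can be given, and the extent depends on which sentence sites followed.

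A reader might infer three stronger conclusions that the documents do not support:

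- **That serious TEAEs are broadly undercounted.** Section 10.9.1 defines an SAE with no exception for laboratory findings, and 10.9.2 exempts only elective or previously scheduled admissions.
- **That discontinuations disappear.** Reasons for stopping treatment are still reported under SAP 6.4.1, and dose modifications with any reason are listed under SAP 6.4.3. What stays open is whether a discontinuation for an untreated laboratory abnormality has an AE record behind it.
- **That the laboratory data are lost.** The values remain listed with CTCAE grade. What is missing is the AE record and the judgements attached to it.

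**What to change.** **Protocol.** Delete or correct the sentence in 10.8.6 that bars recording without intervention, and align the first sentence too, so that 10.5, 10.8.1 and 10.8.6 carry one rule: a laboratory abnormality is recorded as an AE when the investigator judges it clinically significant. Keep the route to the laboratory section of the report for abnormalities not so judged. State in the same rule how to record an abnormality whose only consequence was a study-drug hold or discontinuation. This concerns recording only and changes nothing in Table 1.

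**Reporting.** The SAP's version history is dated 1 December 2022 and the protocol version 3 August 2021, so AEs may already have been collected under the restrictive sentence. If so, note this beside the AE overview table of SAP 6.6.1.2.

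**Cost.** A protocol amendment, which under 13.5 needs investigator, sponsor and IRB/EC approval, and slightly more AE entry at sites. The AE count may rise a little. No new assessments are needed, because the laboratory tests are already scheduled.
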